COVER LETTER

1st June, 2011

PREVENTIHS STUDY
PREvention of VENous Thromboembolism In Hemorrhagic Stroke patients

NCT01573169

PREVENTIHS STUDY

PREvention of VENous Thromboembolism In Hemorrhagic Stroke patients

Introduction

Venous thromboembolism (VTE) is a common life-threatening complication in patients with stroke. In these patients, an average incidence of asymptomatic deep-vein thrombosis (DVT) of 50% has been reported (1). Additionally, pulmonary embolism (PE) has been reported to occur in 2% of patients with stroke (2) and 5% of early deaths after stroke is reported to be due to PE (3). Prospective trials have shown that both unfractionated heparin and low molecular weight heparin are effective in reducing VTE and PE in ischemic stroke patients (4). Current guidelines recommend the use of these agents in ischemic stroke patients with risk factors for VTE (5). The role of anticoagulants for the prevention of VTE in acute hemorrhagic stroke is uncertain and anticoagulant agents have not gained wide acceptance because of concern about possible increases in hematoma enlargement. To support this, a recent meta-analysis has indicated that in patients with hemorrhagic stroke, early anticoagulation is associated with a significant reduction in PE and a non-significant reduction in mortality, with the trade-off of a non-significant increase in hematoma enlargement (6). These meta-analysis results cannot be reliably applied to clinical practice due to the low quality of the studies included.

Objectives

In this multicenter, randomized trial, the use of standard treatment alone (compression stockings and /or intermittent pneumatic compression and /or early mobilization) will be compared with the use of standard treatment plus the

administration of the low molecular weight heparin enoxaparin for the prevention of VTE in patients with acute hemorrhagic stroke. Enoxaparin will be started after 72 hours from stroke onset and will be continued for 10 days. The principal outcome measures will be symptomatic, objectively confirmed VTE or asymptomatic DVT (proximal and/or distal) as assessed by ultrasound examination. Because the use of anticoagulants in patients with hemorrhagic stroke could be associated with a high risk of re-bleeding, the safety of enoxaparin in this clinical setting will also be assessed.

Methods

Study population

The study will be designed as a multicentre, prospective, randomised, open, blinded endpoint clinical trial. Consecutive bedridden patients (a score of 3 or 4 per item 6 of the NIHSS or the impossibility to maintain an upright position such as in the case of ataxia in patients with hemorrhagic cerebellar stroke) 18 years of age or older with primary intracerebral hemorrhage on CT scan or patients with intracranial hemorrhage during treatment with oral anticoagulants (after reversal), will be assessed for eligibility.

Exclusion criteria will include: intracranial hemorrhage due to vascular malformation, bleeding disorders (defined by a prothrombin time more than 30% longer than the control value or a platelet count of less than 100,000 per cubic millimetre), renal failure defined as a clearance of creatinine less than 30, severe hepatic failure, known neoplastic disease, pregnancy, necessity of therapeutic anticoagulant or antiplatelet agents for concomitant disease, participation in

other ongoing clinical trials or patient refusal to consent. The study protocol will be approved by the local ethics committees of the participating hospitals.

Study design and interventions

Patients will be randomized 72 h after the onset of symptoms after having undergone a brain CT scan which will be considered the baseline examination. This CT must exclude a re-bleeding compared to the CT at admission. In the face of re-bleeding, patients will be excluded from randomization. Re-bleeding will be defined as an increase of 10% in the basal volume measured by standardized and validated criteria (9).

Patients will be randomized over the phone using a random list of numbers (even numbers – treatment A; odd numbers – treatment B) to receive enoxaparin 0.4 ml die plus standard therapy (group A) or standard therapy alone (group B). Treatment with enoxaparin is scheduled to last 10 ± 2 days. A venous eco-Color-Doppler examination with a compression test will be performed bilaterally on the lower limbs 10 ± 2 days following the start of treatment. This exam will evaluate the following three points: the common femoral vein at the groin, superficial femoral vein at the mid-thigh and the popliteal vein at the popliteal fossa up until the trifurcation.

Included patients will be visited on a daily basis during their hospital stay in order to monitor any complications as well as check for symptoms and signs of venous thromboembolism. An ultrasound exam of the lower limbs will be performed expediently on any patient having clinical signs of suspected deep venous thrombosis. If this exam results being negative, the patient will undergo a second ultrasound exam according to the timetable set out in the protocol. An

ultrasound exam of the lower limbs and a CT thoracic angiography will be performed expediently on any patient having clinical signs of pulmonary embolism. If these exams result being negative, the patient will undergo a second ultrasound exam according to the timetable set out in the protocol.

A positive result from either the CT thoracic angiography or an ultrasound exam will necessitate a treatment with heparin (unfractionated or at a low molecular weight), warfarin or vena cava filter according to clinical need. Brain CT scan will be performed 10 ± 2 days from the start of treatment or whenever there is a worsening of the clinical condition, defined as an increase of 4 points or more on the NIHSS score. Treatment with heparin will be suspended whenever CT shows an increase of at least 10% in the volume of cerebral hemorrhage, notwithstanding clinical condition. Lesion volume will be measured with the methodology elaborated by Broderick et al. (9). Antithrombotic treatment different from that which is planned by the protocol during the treatment period will be forbidden except in the case of clinical need (i.e. diagnosis of venous thromboembolism). Follow-ups at 30 and 90 days after cerebral hemorrhage will be performed either in-clinic or over the phone in order to monitor for any clinical signs of venous thromboembolism or re-bleeding. All deaths will be recorded.

The final follow-up, at 90 days, will be carried out over the phone by an independent physician blinded to the treatment received. After the treatment period outlined in the protocol (10 ± 2 days), the treating physician will be able to determine future therapy.

In the event of positive ecographs, patients can be treated with heparin (unfractionated or low molecular weight heparin), warfarin or vena cava filter, according to necessity.

Neuroradiological exams as well as pulmonary angio-CTs will be evaluated by the study coordinating centre (University of Perugia) blinded to the clinical condition of the patients.

Venous thrombo-embolic and intra- and extra-cranial hemorrhagic events will be judged blindly on the type of treatment received by the following physicians from the University of Perugia: [name], [name], [name], [name], [name] e [name].

The study will be divided into 3 sections: I. Patients 1-120; II. Patients 121-240; III. Patients 241-406.

Given the complexity of the study, a data safety monitoring board (DSMB) will be responsible for evaluating the progress of the study after the closure of section I. The second evaluation will be performed by the DSMB after the closure of section II. The DSMB will be composed of three independent and external physicians, one of which is a statistician, to the coordinating centre: [name], University of Bologna, [name], University of Perugia and [name], University of Ancona.

Risks of treatments and procedures.

Risks include intra and extracranial hemorrhagic complications associated with heparin use and/or complications such as ulcers and subcutaneous hematomas due to the use of elastic stockings. There are no anticipated risks due to diagnostic procedures, given that all of the exams outlined in the protocol will be usually performed in clinical practice.

Risk-benefit evaluation

Patients with ICH have a reported risk of ~ 20% for thromboembolic complications. The use of prophylactic heparin, where it has been tested on cancer, orthopedic and neurosurgery patients, has reduced the incidences of these events and their respective mortality rates and hospital stays. These studies have also reported an increase in ICH in patients treated with heparin compared to placebo. Whereas, at the end of follow-up, a net benefit, which was statistically significant, remained for those patients treated with heparin compared to those on placebo.

End-points

The primary endpoint of this study will be made up of either: 1) symptomatic venous thromboembolism objectively documented as proximal/distal DVT or pulmonary embolism or 2) asymptomatic proximal/distal DVT documented by ultrasound at the end of follow-up. Diagnostic criteria which has already been validated will be utilized (10).

Secondary end-points:

1. The number of symptomatic and asymptomatic intracranial bleedings as described above in Methods;
2. The number of extracranial bleedings will be divided into two groups: major and minor. Major bleedings will be defined as 1) presence in critical organ sites including the retroperitoneal and intraocular spaces, 2) a reduction of 2 or more gr/dL of hemoglobin or the need to carry out a transfusion of 2 or more units of concentrate red blood cells or 3) fatal bleeding. Medical

intervention, including any interruption of study treatment, will be considered clinically relevant but not a major bleeding for all the events that do not satisfy the above described criteria. All other bleedings will be considered minor;

3. The combined end-point of disability (modified Rankin Scale ≥ 3) and mortality for any cause at 90 days;
4. Mortality alone at 90 days.

For each endpoint event, centres will be required to submit adequate documentation which will be evaluated by the Adjudication Committee.

Statistical analysis

The primary and secondary endpoints will be evaluated with an intention to treat analysis that will include all the randomized patients in both groups which will be treated or not, depending on the randomized group. Differences between the two groups will be calculated using the Chi-square test. The odds ratio, as well as relative risk will be calculated with confidence intervals. All predefined endpoints will be assessed without adjusting for confounding factors. Post-hoc analysis (logistic regression) will be carried out, in the face off any possible un-matching between the two groups, by adjusting for the confounding factors. Logistic regression analysis will be performed by including all the variables and then retaining those having a statistical significance of $p < 0.1$.

The same statistical analyses will be carried out on the per protocol population; that is, those patients that are randomized and assessed for type of treatment actually administered.

Sample size was calculated on the basis of an expected incidence of TVE equal to ~ 20% of non-treated patients, and ~ 10% of enoxaparin treated patients. Both groups will need approximately 203 patients each, in order to evidence a statistical difference of 50% with an alpha-value equal to 0.05 and a beta value of 0.20. The study will be multi-centered with an expected 20 Italian centers participating over a 2-year enrollment period.

Treatment of data

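### The only visible criterion for intracranial bleeding is a net 10% volume increase, so new blood that is offset by haematoma shrinkage, or a small bleed at a new site, need not count in secondary end-point 1

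*Combined protocol and SAP*

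**What the plan says.** All the relevant text on imaging is in Methods, Study design and interventions.

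- **Baseline.** Patients are randomised 72 h after onset, following "a brain CT scan which will be considered the baseline examination". On eligibility: "This CT must exclude a re-bleeding compared to the CT at admission".
- **Criterion.** "Re-bleeding will be defined as an increase of 10% in the basal volume". The sentence goes on to cite reference 9 for the measurement. The reference list as available ends at 6.
- **Follow-up imaging.** "Brain CT scan will be performed 10 ± 2 days from the start of treatment or whenever there is a worsening". Worsening means an NIHSS rise of at least 4 points.
- **Stopping.** "Treatment with heparin will be suspended whenever CT shows an increase of at least 10% in the volume of cerebral hemorrhage". No reference scan is named.
- **Later contacts.** The 30- and 90-day follow-ups, in clinic or by phone, are there to "monitor for any clinical signs of venous thromboembolism or re-bleeding".
- **Reading and judging.** "Neuroradiological exams as well as pulmonary angio-CTs will be evaluated by the study coordinating centre", without knowledge of the patients' clinical condition. Haemorrhagic events are judged blind to treatment, and End-points sends event documentation to an Adjudication Committee.

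Secondary end-point 1 (End-points) counts intracranial bleeds with or without symptoms and takes its definition from Methods. The major and minor bleeding criteria under secondary end-point 2 concern extracranial bleeding only.

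**The concern.** The written rule looks at the change in total volume between two scans. It therefore measures new blood minus whatever the original haematoma has lost since baseline. The only scheduled scan after randomisation comes more than a week after baseline, when some shrinkage may have occurred. A real bleed during treatment could then leave the total less than 10% above the 72 h value, or even below it. A small bleed at a new site, away from the original haematoma, is treated in the same way.

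The Objectives make the safety of enoxaparin a question of the trial because of the feared risk of re-bleeding, and secondary end-point 1 explicitly includes silent bleeds. In practice the scheduled CT has to find those. The later contacts look for clinical signs, so an asymptomatic bleed that goes uncounted on that CT is not recovered. If such bleeds are lost equally in both arms, the relative risk is roughly kept but the absolute difference shrinks. The absolute difference is what has to be weighed against venous thromboembolism prevented.

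**Working it through.** **Inputs.** From Methods: a threshold of 10%, the 72 h CT as baseline, and a scheduled CT at 8 to 12 days from the start of treatment. Assumed, because the documents do not give them: shrinkage s of the original haematoma between the two scans (0 to 30% shown) and, for the mL illustration only, a 72 h volume of 30.0 mL. It is also assumed that all sites of bleeding are added together in the measured volume.

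**Timing.** With treatment starting at 72 h (day 3), the scheduled CT falls between 3 + 8 = 11 and 3 + 12 = 15 days from onset.

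**Threshold.** Let V be the 72 h volume and b the new blood present on the later scan. The measured total is (1 − s)V + b. The rule is met when

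(1 − s)V + b ≥ 1.10 V, that is, b ≥ (0.10 + s)V.

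At s = 0 this returns the protocol's own 10%. For other values of s:

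| Assumed s | Smallest b as a share of V | Smallest b if V = 30.0 mL | Volume just before the bleed | b as a share of that volume |
|---|---|---|---|---|
| 0 | 10% | 3.0 mL | 30.0 mL | 10% |
| 10% | 20% | 6.0 mL | 27.0 mL | 6.0/27.0 = 22% |
| 20% | 30% | 9.0 mL | 24.0 mL | 9.0/24.0 = 38% |
| 30% | 40% | 12.0 mL | 21.0 mL | 12.0/21.0 = 57% |

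**Break-even.** A bleed of size b stops meeting the rule once s exceeds b/V − 0.10:

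- b = 15% of V: 0.15 − 0.10 = 5% shrinkage
- b = 20% of V: 0.20 − 0.10 = 10% shrinkage
- b = 30% of V: 0.30 − 0.10 = 20% shrinkage

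**New site.** Nothing in the formula depends on where b lies, so a bleed at a new site faces the same threshold, (0.10 + s)V. Even at s = 0, one smaller than 10% of V does not count.

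**Effect on the comparison.** If a fraction m of true bleeds goes uncounted in both arms, risks p_A and p_B are observed as (1 − m)p_A and (1 − m)p_B. Their ratio is unchanged, and their difference is multiplied by (1 − m). The documents give nothing from which m could be estimated.

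**The case against.** The strongest reply is that the definition closes the eligibility paragraph and is not necessarily the whole definition of secondary end-point 1. Methods also provides central CT reading and blinded judging, and an Adjudication Committee follows. Nothing stops those readers from counting visible new blood whatever the total volume. This stands in part. A reader might infer that the protocol excludes such bleeds, and the documents do not support that. They leave the matter to the reader's judgement, with only the net volume rule in writing. Blinding guards against bias by arm, but it does not supply a definition.

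Second, the measurement method comes from reference 9, which cannot be seen. It may distinguish new from old blood. The point is therefore limited to what is visible.

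Third, shrinkage is assumed. This stands: no figure in the documents shows that any bleed in this trial would be missed, and at s = 0 only new blood below the intended 10% goes uncounted.

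Fourth, a volume threshold is objective, which is useful in an open-label trial, and a judgement of new blood is less so. That is a reason to keep the 10% rule and report the new item beside it.

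Fifth, a bleed that raises the NIHSS by 4 or more prompts its own CT, possibly well before days 11 to 15. This also stands, and it is why the point concerns mainly asymptomatic bleeds.

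**Conclusion.** The point holds in a limited form. Read literally, with the 72 h CT as baseline, the only visible criterion leaves out new blood below (0.10 + s) of the 72 h volume, whether inside the original haematoma or at a new site. The algebra is exact. The practical size is unknown because it depends on s and on the distribution of bleed sizes, and the documents give neither. The effect is confined to one secondary safety end-point. The primary endpoint and the sample size, which rest on thromboembolism, are not touched.

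Three stronger readings are not supported:

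- **Bias towards enoxaparin.** The rule applies to both arms, and nothing in the documents shows that the loss would differ between them.
- **A failed stopping rule.** "Treatment with enoxaparin is scheduled to last 10 ± 2 days", so the scheduled CT arrives at about the end of treatment. The rule matters for stopping mainly on a CT done for clinical worsening, and nothing prevents the physician from stopping then. Adding a more subjective trigger is a debatable trade-off, and no change is proposed.
- **An undefined baseline.** The protocol names the 72 h CT as baseline just before it refers to basal volume, which nearly settles the matter. Saying so explicitly is only a clarification.

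**What to change.** Keep the 10% rule and state in Methods that growth after randomisation is measured from the 72 h CT. Add to secondary end-point 1 a yes/no item for the blinded central reader already planned: new blood not present on the 72 h CT, meaning a new site or clearly fresh blood within the original haematoma. Tabulate this item by arm beside the 10% component, not merged with it.

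The cost is one clarifying sentence in Methods, one sentence in End-points and one item on the CT reading form. No extra scan or staff is needed. The downside is that the item is more subjective than a volume. It may give false positives, and by days 11 to 15 it may miss bleeds that are no longer recognisable as fresh. Separate reporting keeps any false positives visible and leaves the volume-based result intact.

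### Allocation by even or odd random numbers, with no blocking or stratification stated and an unadjusted primary test, leaves balance within about 20 centres to chance; the cost is precision, not bias.

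*Combined protocol and SAP*

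**What the plan says.** **Allocation.** Under Study design and interventions, the combined protocol and SAP says: "Patients will be randomized over the phone using a random list of numbers (even numbers – treatment A; odd numbers – treatment B". Group A receives enoxaparin plus standard therapy and group B standard therapy alone. The document does not say how the list is generated, what range the numbers cover, whether they can repeat, who holds the list, or whether each centre has its own. Blocks, strata and minimisation are not mentioned.

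**Centres and size.** Statistical analysis gives "an expected 20 Italian centers participating over a 2-year enrollment period" and "Both groups will need approximately 203 patients each". The last recruitment section, "III. Patients 241-406", confirms a total of 406.

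**Analysis.** Statistical analysis specifies a chi-square test, with all predefined endpoints unadjusted. Logistic regression is offered post hoc if the groups turn out to be unmatched. Centre is not named as a covariate.

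**Where centres could differ.** Objectives defines standard treatment as "compression stockings and /or intermittent pneumatic compression and /or early mobilization". Asymptomatic DVT on leg ultrasound is a component of the primary endpoint. Study design and interventions sends brain imaging and pulmonary CT angiography to the coordinating centre for reading; leg ultrasound is not listed. Thromboembolic events are adjudicated blind to treatment.

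**The concern.** On its natural reading, taking treatment from the parity of a random number is simple randomisation. With around 20 patients per centre it will often leave some centres clearly lopsided. If centres also differ in underlying event rate, that lopsidedness adds noise to the treatment comparison, and an unadjusted test does nothing to remove it.

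The text leaves room for such differences. The background measures may be combined in any way, and no central reading of leg scans is described. Blinded adjudication can check a reported thrombus, but the plan does not say that negative scans are re-read, so a missed thrombus would stay missed.

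What is at stake is precision in a trial with little margin. The design expects 203 × 0.20 + 203 × 0.10 = 60.9 primary events and states no dropout allowance. Credibility is also affected: in an open trial, readers will look for visible balance across sites.

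**Working it through.** **1. The plan's sample size.** Inputs from Statistical analysis: "an expected incidence of TVE equal to ~ 20% of non-treated patients, and ~ 10% of enoxaparin treated patients", "with an alpha-value equal to 0.05 and a beta value of 0.20". The plan does not state sidedness; two-sided is assumed. With a pooled variance and no continuity correction (mean rate 0.15):

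n = [1.960 × √(2 × 0.15 × 0.85) + 0.842 × √(0.20 × 0.80 + 0.10 × 0.90)]² / 0.10² = 199 per arm.

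This is within 3% of the stated 203. At 203 per arm, power is 80.8%.

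**2. Overall arm sizes.** If each number is independently even or odd, the size of one arm is Binomial(406, 0.5):
- SD = √406 / 2 = 10.1; 95% range 183 to 223.
- P(arms differ by 20 or more) = 0.346.
- Power at 183/223 is 80.0% or 80.8%, depending on which arm is smaller. Averaged over all splits it is 80.7%.

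The most that a 183/223 split costs is therefore 80.8 − 80.0 = 0.8 points.

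**3. Splits within centres.** Equal recruitment is an assumption: 406 / 20 ≈ 20 patients each. Two-sided binomial probabilities:

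| Centre size | Split or worse | Probability | Expected among 20 such centres |
|---|---|---|---|
| 20 | 14:6 | 0.115 | 2.3 |
| 20 | 13:7 | 0.263 | 5.3 |
| 10 | 8:2 | 0.109 | – |
| 5 | 5:0 | 0.0625 | – |

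The probability that at least one of 20 centres has a 14:6 split or worse is 1 − (1 − 0.115)^20 = 0.91.

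**4. The other reading of the list.** A shuffled list of the numbers 1 to 406 contains exactly 203 even and 203 odd numbers. A centre's split is then hypergeometric (20 drawn from 406, of which 203 are even). P(14:6 or worse) = 0.106, or about 2.1 centres of 20. Fixing the totals does almost nothing for balance within centres.

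**5. Effect on the primary test.** The documents give no between-centre variation, so a range was assumed: normal centre effects on the logit scale with SD 0, 0.5 or 1.0. Marginal rates were held at 20% and 10%, with 20 centres of 20 patients (400 in total) and 40,000 simulated trials per cell. To show the scale: for SD 0.5 the mean control logit is −1.459, so control rates at one SD below and above are 12% and 28%; for SD 1.0 it is −1.650, giving 7% and 34%.

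| Centre SD | Quantity | Simple, chi-square (the plan) | Simple, Mantel-Haenszel | Blocked by centre, chi-square | Blocked by centre, Mantel-Haenszel |
|---|---|---|---|---|---|
| 0 | Power | 80.8% | 78.8% | 81.4% | 80.7% |
| 0.5 | Power | 80.5% | 79.9% | 81.4% | 81.9% |
| 1.0 | Power | 80.5% | 83.0% | 81.8% | 84.5% |
| 0 | Type I error | 5.1% | 5.0% | 4.9% | 5.0% |
| 0.5 | Type I error | 5.2% | 4.9% | 4.6% | 5.0% |
| 1.0 | Type I error | 4.9% | 4.9% | 3.6% | 4.9% |

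Three things follow. The plan as written holds its error rate. Blocking while keeping the unadjusted chi-square makes the test conservative when centres differ (3.6% at SD 1.0). Stratifying the test without balancing the allocation loses about 2 points if centres do not differ. Doing both gains the most when centres differ and costs next to nothing when they do not.

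**The case against.** The strongest reply is that simple randomisation is valid and is the least predictable scheme available, which matters in an open trial. Its chance imbalances are already covered by the test's error rate. Blocking alone gains only about 1 point of power (80.5% to 81.4% or 81.8%). Blocking also makes some allocations guessable, and that can cause selection bias, a worse fault than noise. The plan has safeguards too: blinded adjudication, one fixed bilateral scanning procedure for every patient, validated diagnostic criteria, and post-hoc regression if the groups prove unmatched.

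Much of this stands, and it rules out three stronger readings that a reader might infer.
- **That centre is confounded with treatment.** It is not. The imbalance is random in direction, and type I error stayed at 4.9% to 5.2% for every centre SD tried.
- **That prophylaxis and sonography do differ between centres.** The text permits this but does not say it. Nor does it say who performs the leg scans or who chooses the background measures.
- **That failing to reach 203 per arm is a material fault.** The plan says approximately 203, a shuffled list would give it exactly, and a 183/223 split costs at most 0.8 points of power.

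The reply does not supply any provision for centre. The regression is post hoc, keeps variables by their p-value and does not name centre. The predictability objection bears on how balance is achieved: minimisation with a random element, or hidden varying blocks, largely answers it.

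**Conclusion.** The point holds as a loss of precision. Nothing in the plan secures balance within centres, and the primary analysis does not recover what chance imbalance loses. Under equal recruitment, about 2 of 20 centres would be split 14:6 or worse whichever way the number list is read.

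The gain available from balancing by centre and stratifying the test is about 1 point of power at a centre SD of 0.5 and about 4 points at 1.0. If centres do not differ, there is essentially no gain. These figures rest on assumed centre SDs, equal centre sizes, the plan's own event rates and a two-sided test. The change is worth making because it is cheap and cannot be made once patients are allocated; the trial's validity does not depend on it.

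**What to change.** Before the first patient is randomised:

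1. **Allocation.** Replace the even/odd list with concealed telephone allocation balanced by centre. Use either minimisation with a random element or permuted blocks of varying size that are not disclosed to sites. State how the sequence is generated, who holds it, and that the patient is registered before the assignment is released.
2. **Analysis.** Prespecify centre in the primary analysis, for example a centre-stratified Mantel-Haenszel test with the matching stratified effect estimate and confidence interval. State in advance how very small centres will be pooled. This belongs with the first change, because an unadjusted chi-square after centre-balanced allocation is conservative when centres differ.

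The cost is some programming and a short amendment to Study design and interventions and to Statistical analysis. No extra patients or procedures are needed, and the required sample size does not change. The downside is slightly more predictable allocation in an open trial, limited by the random element or the hidden block sizes.

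### The primary endpoint counts asymptomatic distal DVT, but the only ultrasound scheduled for every patient stops at the popliteal trifurcation, and none is scheduled at the end of follow-up

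*Combined protocol and SAP*

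**What the plan says.** All references are to the combined protocol and SAP.

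- **Objectives.** The principal outcome includes "asymptomatic DVT (proximal and/or distal) as assessed by ultrasound examination".
- **End-points.** The primary endpoint has two components: symptomatic, objectively documented VTE (proximal or distal DVT, or PE), and "asymptomatic proximal/distal DVT documented by ultrasound at the end of follow-up". The diagnostic criteria are cited to reference 10, which cannot be checked in the supplied text.
- **Study design and interventions, scheduled scan.** One bilateral examination takes place 10 ± 2 days after the start of treatment. It evaluates three sites: the common femoral vein, then the "superficial femoral vein at the mid-thigh and the popliteal vein at the popliteal fossa up until the trifurcation".
- **Same section, unscheduled scans.** "An ultrasound exam of the lower limbs will be performed expediently on any patient having clinical signs of suspected deep venous thrombosis". For suspected PE, an "ultrasound exam of the lower limbs and a CT thoracic angiography will be performed expediently on any patient having clinical signs of pulmonary embolism". Neither sentence says which veins are to be examined. After negative results the timetable scan still follows: "If these exams result being negative, the patient will undergo a second ultrasound exam according to the timetable set out in the protocol".
- **Same section, follow-up.** The 30- and 90-day contacts, in clinic or by phone, are made "in order to monitor for any clinical signs of venous thromboembolism or re-bleeding". "The final follow-up, at 90 days, will be carried out over the phone".
- **Statistical analysis.** The planning rates are about 20% and 10% VTE, with about 203 patients per group, alpha 0.05 and beta 0.20. The rates are not split by site or by symptoms.

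**The concern.** Part of the primary endpoint has no scheduled measurement. A patient without symptoms whose thrombus lies wholly below the trifurcation is recorded as event-free unless someone happens to look further. Reported as written, the trial would give a result for proximal and distal DVT, although its routine scan does not examine the distal veins.

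The gap also leaves room for inconsistent practice. About 20 centres are expected. Some may scan the calf because the endpoint names distal DVT; others may stop at the trifurcation because the scan description does. Distal is not defined, so the adjudicators have no stated rule for a calf thrombus found outside the three sites, or for one at the trifurcation itself.

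**Working it through.** **1. Is there a scheduled look at the distal veins?**

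| Source | Veins | When | Who |
|---|---|---|---|
| Endpoint, asymptomatic component | Proximal and distal | End of follow-up | All patients |
| Scheduled scan | Three sites, ending at the trifurcation | Day 10 ± 2 | All patients |
| Symptom-driven scans | Not specified | On suspicion of DVT or PE | Suspected cases only |
| 30- and 90-day contacts | No scan scheduled | Days 30 and 90 | All patients |

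No row gives every patient an examination below the trifurcation. The description of the scheduled scan as bilateral on the lower limbs does not widen it, because the next sentence lists the three sites. Symptom-driven scans could find a calf thrombus, but they are not systematic. On timing, the only scan that every patient is due is at day 10 ± 2, and none is scheduled at day 90.

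**2. The plan's own sample size.** Inputs from Statistical analysis: p₁ = 0.20, p₂ = 0.10, alpha 0.05 (two-sided assumed, as the plan does not say), power 0.80. With pooled variance and mean rate p̄ = 0.15:

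n = [1.960 × √(2 × 0.15 × 0.85) + 0.842 × √(0.16 + 0.09)]² / 0.10² = (0.990 + 0.421)² / 0.01 ≈ 199 per group.

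This is within 3% of the stated 203. The exact binomial power of the uncorrected chi-square test at 203 per group is 81%.

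**3. What unseen events could do to power.** The documents give neither the share of events that the scan would miss nor how those events respond to enoxaparin. So let *u* be the assumed unseen share of control events and *RR* the assumed relative risk of the unseen events. Hold the overall rates at 20% and 10%. Then:

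- visible control rate = 20% × (1 − u)
- visible enoxaparin rate = 10% − 20% × u × RR

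For example, u = 25% and RR = 0.3 give 20% × 0.75 = 15% and 10% − 20% × 0.25 × 0.3 = 8.5%.

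| u | RR of unseen events | Visible rates | Power at 203 per group | n per group for 80% power |
|---|---|---|---|---|
| 0 | – | 20% / 10% | 81% | 199 |
| 10% | 0.3 | 18% / 9.4% | 72% | 250 |
| 10% | 0.5 | 18% / 9.0% | 76% | 226 |
| 10% | 0.7 | 18% / 8.6% | 80% | 204 |
| 10% | 1.0 | 18% / 8.0% | 86% | 177 |
| 25% | 0.3 | 15% / 8.5% | 53% | 385 |
| 25% | 0.5 | 15% / 7.5% | 67% | 278 |
| 25% | 0.7 | 15% / 6.5% | 80% | 208 |
| 25% | 1.0 | 15% / 5.0% | 93% | 141 |

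Power is back at 81% when the relative risk of the unseen events is about 0.74 (u = 10%) or 0.72 (u = 25%), and higher above that. The table applies only if the planning rates include the unseen events. If they already describe what the three-site scan detects, the first row holds.

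**The case against.** The strongest defence is that little harm is demonstrated. The scheduled scan is identical in both arms, events are adjudicated blind, and a report that names the segments examined would largely cure the over-wide label. On timing, the day 10 ± 2 scan is the only workable reading, since no other is scheduled. Much of this stands, and it limits how serious the point is. It does not remove the mismatch: the primary endpoint still names something that the schedule does not measure.

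Three stronger readings are tempting, and the documents do not support them.

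- **That the trial is underpowered.** The shares and relative risks in the table are assumptions. The direction of the effect is unknown, and there is no effect at all if the planning rates exclude the unseen events.
- **That the comparison is biased, or that it is safe from bias.** The common scheduled scan creates no bias by itself. But treatment is open, and symptom-driven scans have no stated vein limit, so calf findings could differ by centre or arm. Blind adjudication cannot recover veins that nobody examined, and the blinded central reading is described for neuroradiology and pulmonary CT angiography, not for ultrasound. The documents establish neither reading.
- **That the 50% asymptomatic DVT cited in the Introduction shows what the 20% planning rate covers.** The 50% refers to stroke patients in general. The 20% matches the figure for thromboembolic complications in intracerebral hemorrhage given under Risk-benefit evaluation. The populations differ, so nothing follows.

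Reference 10 might define distal DVT. It cannot be read here, and a diagnostic criterion would not add a vein to the list of sites scanned.

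**Conclusion.** The mismatch is in the text and needs no assumption. Asymptomatic isolated distal DVT belongs to the primary endpoint but is not systematically ascertained, and the endpoint's stated time has no scan. A conclusion about asymptomatic distal DVT would be wider than the data.

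The effect on power is unknown. The range of about 53% to 93%, against 81%, rests wholly on the assumed shares (10% to 25%) and relative risks (0.3 to 1.0) and is illustration only. Variation in calf findings between centres or arms is possible but not shown. The point should be corrected before results are seen, because it concerns the primary endpoint and is cheap to settle. It is not a critical fault, since neither bias nor loss of power has been demonstrated.

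**What to change.** Amend the wording as follows.

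1. Define the asymptomatic component as DVT at the three examined sites on the day 10 ± 2 scan, or at those sites on an earlier symptom-driven scan. The second clause matters because the timetable scan is promised only after a negative earlier one.
2. Remove the end-of-follow-up timing from this component, and change the Objectives to match.
3. Keep symptomatic, objectively documented distal DVT in the symptomatic component. Report asymptomatic distal DVT found outside the three sites separately.
4. Define distal, and say how thrombus at the trifurcation is classed.
5. Have the blinded adjudicators fix in advance how distal DVT on a suspected-PE scan is classed. It should not become a non-event by default when PE is not confirmed: such a patient may be treated and not rescanned, and the symptomatic component could reasonably include the finding.
6. In the sample-size paragraph, state whether the 20% and 10% rates include asymptomatic isolated distal DVT. If they do, restate the power of 203 per group for the narrowed endpoint.

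The cost is a narrower endpoint claim, possibly a less favourable stated power, and a protocol amendment through the local ethics committees of about 20 centres. No procedure is added. Adding a calf examination to the scheduled scan would equally reconcile the sections and keep the wider endpoint, but it is an extra procedure at every centre.
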